#### 2.1.2 Primary Objectives

### Theme 1

2.1.2.1 Feasibility of home high-density EEG (primary objective);

2.1.2.2 Acceptability of home EEG;

#### Theme 2

2.1.2.3 Feasibility of blood biomarkers for AD;

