- iv) Sleep dependent memory testing a long-term memory word test delivered by the researcher on either the second or third evening of testing (order counterbalanced)
- v) Acceptability participants will be asked to complete a brief questionnaire within 1 week of their final testing session to feedback on their experience (See appendix 2).

### For Substudy 2

Venepuncture of 5-10 ml blood biomarkers taken for analysis of biomarkers (P-tau & NFL, GFAP and abeta42/40, and possibly others in future). In all participants undergoing LP, this will be at the time when bloods are taken alongside LP in any case (i.e. there will be not an extra venepuncture, just more blood drawn). In very rare situations, for example, participants who have another form of biomarker testing (e.g. PET scanning), a new venepuncture will be needed.

As an optional addition, the collected blood sample will also be analysed for *APOE* genotype. The venepuncture already being arranged for blood biomarker analysis will provide a sufficient sample for the additional *APOE* analysis. The *APOE* analysis therefore does not require an additional blood sample/procedure.

As an optional addition, an extra < 5 ml of CSF will be taken during the routine LP for analysis and storage, as long as this does not prolong the procedure by more than 1 minute.

All patients will have had a MoCA cognitive test as part of routine care within 3 months of CSF collection. In the very rare case that this has not happened as part of routine clinical care, we will also carry out a MoCA as close as possible in time to their lumbar puncture (taking into account they might be nervous on the day of the procedure, we may do this at a different hospital visit). As an alternative, we will offer the opportunity to complete the MoCA test remotely via video call and save the need for an additional hospital visit. Several studies have demonstrated that administering the MoCA remotely via video call is a valid and reliable alternative to a face-to-face assessment.

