### 6.4 Participant Guidance for Assessments

### 6.4.1 Reminders and support for assessments

[figure not shown]
A researcher will visit the participants house to place the EEG on each night of the study. This will involve applying the cap, fixing the electrodes and doing an initial check of data quality.

SleepAD Protocol v6.0 6th September 2024

The researcher will deliver the cognitive tasks and be available by telephone for the entire study duration in case there are queries.

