### 8.2 Frequency of Data Collection

### For substudy 1

Data will be collected during a one-off eligibility telephone conversation, an initial visit, over 3 nights of sleep EEG and then with acceptability questionnaire within 1 week of overnight testing.

Baseline data collected during the eligibility telephone conversation and initial visit will be entered by researchers into paper case report forms and then into REDCAP (electronic data capture system) or directly into REDCap. Data collected during the Study Assessment Period will comprise raw electronic data from measurement devices which will be downloaded onto secure computers at the end of the assessment period and memory test results that will be uploaded onto REDCap after testing.

#### For Substudy 2

Demographic and clinical data will be extracted from electronic medical records. Venepuncture will occur only once at the same time as clinical LP.

SleepAD Protocol v6.0 6th September 2024

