#### 11.5 Participant Burden

Overall, this study has a relatively low burden on participants, with the focus being obtaining data (sleep patterns and memory tests) that reflects everyday life for the participants. The technology planned to measure these patterns is specifically designed to be non-invasive, with the exception of a one-off blood test for some participants.

Screening and baseline consultations will be conducted face to face or remotely permitting us to flexibly mitigate COVID-19 or future pandemics.

All visits to the patient's home should last no longer than two hours. All equipment and study materials will be collected from the participants when data collection has ended.

The cognitive tests will require mental effort on the part of participants. Participants are free to stop the test at any time and this will be re-iterated prior to the start of the test.

The sleep diary will only need to be completed each morning. This should take no more than 2 minutes to complete each day.

SleepAD Protocol v6.0 6th September 2024

Venepuncture causes a brief stinging sensation that is usually well tolerated and occasionally triggers syncope in the minute or two afterwards, or causes a bruise later on. Participants will be seated during venepuncture and will be observed and offered suitable refreshments afterwards in case of any immediate syncope.

We will not be able to meaningfully feedback the blood biomarker or CSF/ plasma orexin results as we are using a research only laboratory without validated normal ranges which we will extrapolate from the clinic laboratory at UCL. Therefore we will not be able to disclose AD risk on the basis of blood biomarkers – thus avoiding potential participant burden to decide if they would like to know.

Similarly, we will not be able to meaningfully feedback the results of the *APOE* genotyping. The results will be for research purposes only and not performed as a clinical test. We are not undertaking the genetic testing in a validated clinical laboratory, and NICE guidelines specifically advise against disclosing the outcome. As we will not be disclosing AD risk on the basis of genotyping this avoids adding potential participant burden to decide if they would like to know.

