# Comments

Q26	Do you have any additional comments regarding your sleep?	

Appendix 2

**Sleep AD experience questionnaire** The questionnaire is designed using the Unified Theory of Acceptance and Use of Technology (UTAUT) model to determine the factors that determine user acceptance of technology these include performance expectancy, effort expectancy, social influence, attitude, and facilitating conditions.

Question	Response format
How did you feel about taking part in the SleepAD study?	Free text
Did your experience of wearing the EEG match your expectations (or was it better or worse)?	Free text
What did you think about wearing the EEG device before testing?	Free text
Did you encounter any difficulty or notice benefits from using the EEG device?	Free text
Do you think it's a good/interesting idea to use an EEG device to measure your sleep and do blood testing?	Free text
Did anyone encourage you to continue the study?	Free text
What did your family/friends think about you getting involved in this study?	Free text
How did you find the process of blood testing?	Free text
Would anything make the process easier for you in the future?	Free text

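### Two of the nine acceptability items ask for expectations of the EEG only after all recordings, in people with MCI or mild AD, and no earlier record exists to check them against

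*Protocol*

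**What the plan says.** Section 2.1.2 lists "2.1.2.2 Acceptability of home EEG" under Primary Objectives, and the Theme 1 primary hypothesis in section 2.2.1 couples acceptability with feasibility.

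Section 6.3 gives the timing for Sub-Study 1: "participants will be asked to complete a brief questionnaire within 1 week of their final testing session to feedback on their experience". Section 8.2 agrees, placing data collection "over 3 nights of sleep EEG and then with acceptability questionnaire within 1 week of overnight testing".

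Appendix 2 has nine free-text items. It is built on a technology-acceptance model whose stated constructs are "performance expectancy, effort expectancy, social influence, attitude, and facilitating conditions". Item 2 asks "Did your experience of wearing the EEG match your expectations (or was it better or worse". Item 3 asks "What did you think about wearing the EEG device before testing". Item 5 asks in one sentence whether using EEG for sleep and doing blood testing are a good or interesting idea.

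Eligibility (sections 4.2 and 4.3) requires MCI due to AD or mild AD. MoCA scores of 11/30 and above are admitted, and lower ones at the investigator's discretion.

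On contacts, section 6.4.1 says "A researcher will visit the participants house to place the EEG on each night of the study".

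**The concern.** An expectation is informative only if it is recorded before the experience it refers to. Asked afterwards, the answer mixes what the person thought then with what happened since. In a population selected for MCI or mild AD, plain forgetting is added to that hindsight. The questionnaire claims to measure expectancy constructs, yet the expectancy answers come from the same sitting as the verdict on the experience, with no independent record to compare them with.

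The programme is meant to prepare larger sleep trials. There, what people think of the device before they have tried it bears on who agrees to take part. If that view is reconstructed, the study cannot tell initial reluctance that faded from reluctance that was never there. The timing and wording are fixed in the protocol, so this is not a matter left to an analysis plan.

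The combined item is a smaller, separate fault. The protocol states one primary hypothesis for EEG and another for blood biomarkers, and a single answer to item 5 may not be attributable to either.

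**Working it through.** No sample-size or power figure bears on this point, so the check is textual, with one count, one interval and one piece of algebra on direction.

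1. **Is there an earlier record of expectations?** The baseline assessments in section 6.2 cover the MoCA, sleep scales, mood, anxiety and apathy scales, restless legs, the SleepAD sleep questionnaire (Appendix 1), demographics and blood. None asks about expectations of the EEG. The one self-report tied to each night is the Consensus Sleep Diary (sections 6.3 and 11.5), which is not presented as an acceptability measure. So Appendix 2 is the sole source.

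2. **How many items are affected?** Items 2 and 3 need the pre-exposure view: 2 of 9, or 2/9 = 22%. The other seven concern the experience, other people's influence, present opinion or suggestions. Questions about the experience can only follow it.

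3. **How old is the pre-test view when it is asked for?** Assume three consecutive nights, which the protocol does not state. From the first fitting to the end of night 3 is about 3 days, and the questionnaire follows 0 to 7 days later: 3 + 0 = 3 days to 3 + 7 = 10 days. If nights are spread out or repeated, the interval is longer. Section 11.4.2 gives a maximum enrolment of 1 month, and section 9.5 allows a repeat night within a 3-month study period. The one-week window starts only at the final session.

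4. **Which way would the bias go?** Let *b* and *w* be the true shares who found the EEG better or worse than expected, and let fractions *r* and *s* of these groups rebuild their expectation to fit the experience and answer that it matched.
   - Reported matched share = (1 − *b* − *w*) + *rb* + *sw*, which cannot be lower than the true share.
   - Reported better-minus-worse balance = (1 − *r*)*b* − (1 − *s*)*w*. Its change from *b* − *w* is *sw* − *rb*.
   - The sign of *sw* − *rb* depends on four quantities that the documents do not give. Lost answers of better make the device look less welcome; lost answers of worse make it look more so. Simple forgetting can add error either way.

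5. **What depends on it?** Section 10.2 judges EEG feasibility by the proportion of missing data, which uses no recall. Only the acceptability analysis draws on these items.

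**The case against.** The strongest reply is that most of the questionnaire is sound where it stands. Seven of nine items need no pre-exposure view. The one-week limit is a maximum, and same-day completion is allowed. Participants must have full capacity, which under section 5.3 includes retaining information long enough to weigh it. Night-level problems are not left wholly to the final questionnaire: adverse events are asked about at each contact (section 12), a diary covers each night, and a researcher attends each evening. Within Primary Objectives, the explicit label of primary objective is attached to EEG feasibility alone.

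All of this stands, and it limits the point. It does not answer it: none of those contacts records an expectation, and completing the form on the last day would still put item 3 after the exposure.

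A reader might infer that the whole acceptability objective rests on unreliable recall. The item count does not support that. A reader might also infer that acceptability will be overstated. Step 4 shows that the direction is open, and an answer that the experience matched expectations is not the same as finding it acceptable. Any percentage would need invented rates for a quantity that section 10.2 does not define.

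It is also tempting to move the whole questionnaire to equipment collection. Section 11.5 says "All equipment and study materials will be collected from the participants when data collection has ended", and the questionnaire is itself part of data collection, so an earlier collection visit is not clearly planned. Under section 6.3 blood may be taken at a separate appointment, possibly later, which would leave the blood item unanswerable.

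On item 5, free text lets respondents separate the two procedures, and item 8 asks about blood testing alone. The fault is minor, but splitting the item costs nothing.

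**Conclusion.** The point holds in a limited form. Items 2 and 3 of Appendix 2 are open to recall error and hindsight because the expectation is requested only after all EEG nights and was never recorded beforehand. This weakens the expectancy part of objective 2.1.2.2. It does not touch EEG feasibility and does not invalidate the other items.

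The size is 2 of 9 items, with a pre-test view about 3 to 10 days old if the nights are consecutive, and older if they are not. The effect on the results cannot be quantified from the documents, and its direction is unknown. That recall is impaired enough to matter is an inference from the eligibility criteria, not something the protocol measures. The change is worth making because the loss cannot be repaired at analysis and the remedy is nearly free.

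**What to change.** - Take the pre-test item out of the end questionnaire, put it in the present tense, and ask it on the first evening before the cap is fitted.
- Keep the match-to-expectation item in the end questionnaire, and interpret it against the answer recorded on the first evening.
- Split item 5 into one EEG item and one blood-testing item.
- Optionally, add a one-line comfort or difficulty item to the daily sleep diary.
- Leave the remaining items in the existing one-week window, with an instruction to complete them as early as possible.

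The cost is an amendment to section 6.3, section 8.2 and Appendix 2, and a few minutes at a visit already planned. The main downside is a small risk of courtesy answers in front of the researcher who fits the cap. Section 8.1.1 already provides for the acceptability questionnaire on paper, so participants who can do so may write the answer themselves.

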### 6.4 Participant Guidance for Assessments

### 6.4.1 Reminders and support for assessments

[figure not shown]
A researcher will visit the participants house to place the EEG on each night of the study. This will involve applying the cap, fixing the electrodes and doing an initial check of data quality.

SleepAD Protocol v6.0 6th September 2024

The researcher will deliver the cognitive tasks and be available by telephone for the entire study duration in case there are queries.

### 7 SUMMARY OF TRIAL TIMELINE

### 7.1 Participant Sub-Study 1 Timeline

### 8 DATA COLLECTION

Within 3 months

# 8.1 Methods Of Data Collection

#### 8.1.1 Paper based records

Data will be collected on paper during the initial eligibility check, throughout the first stage of the initial consultation and for the acceptability questionnaire.

#### 8.1.2 Electronic records

Where possible, questionnaire data will be entered directly into an electronic data capture system (REDCap) during the consultation. Data collected on paper records will be entered into the same system following the consultation where appropriate.

#### 8.1.3 Measurement Devices

Raw data from measurement EEG will be downloaded electronically.

### 8.2 Frequency of Data Collection

### For substudy 1

Data will be collected during a one-off eligibility telephone conversation, an initial visit, over 3 nights of sleep EEG and then with acceptability questionnaire within 1 week of overnight testing.

Baseline data collected during the eligibility telephone conversation and initial visit will be entered by researchers into paper case report forms and then into REDCAP (electronic data capture system) or directly into REDCap. Data collected during the Study Assessment Period will comprise raw electronic data from measurement devices which will be downloaded onto secure computers at the end of the assessment period and memory test results that will be uploaded onto REDCap after testing.

#### For Substudy 2

Demographic and clinical data will be extracted from electronic medical records. Venepuncture will occur only once at the same time as clinical LP.

SleepAD Protocol v6.0 6th September 2024

#### Follow-up checks of medical records

Medical records from participants in both substudies will be checked again at 2 years and at 5 years after involvement in the study. This will only include available records from those participants in the pre-clinical/MCI phase at time of participation in the study. In both substudies, the date will be measured from the date of the last participant's venepuncture. This follow-up data will be extracted to identify whether the pre-clinical / MCI diagnosis has changed to a dementia diagnosis.

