#### Accuracy

For people with Mild AD dementia or MCI due to AD reference ranges are available from research cohorts and P-tau 181 alone has an Area Under Receiver Operating Characteristic curve (AUROC) of 0.80 compared to amyloid PET [23] and the combination of NFL and P-tau 181 has an AUROC of 0.88 compared to delayed verification of AD (sensitivity 83-88%, specificity 82-83%) to identify people who have progressive AD pathology as a cause of their MCI at baseline. Simple cognitive tests carried out in clinic such as the Montreal Cognitive Assessment have 90% and 100% sensitivity for MCI and mild AD dementia respectively, with specificity varying according to the cohort (up to 87% when comparing to healthy control in a research cohort) [24]. For people without AD – cerebrospinal fluid (CSF) biomarkers have a very high negative predictive value (94% on a real-world sample after median 4.7 years follow-up). Modelling suggests that combining blood biomarkers with simple cognitive tests will be more sensitive and specific than either test alone.

SleepAD Protocol v6.0 6th September 2024

As blood biomarkers make large scale interventional studies possible in AD at vastly reduced expense (as we can avoid CSF testing or PET scanning), new therapeutic targets for intervention can be tested more rapidly.

The value of blood biomarkers is ultimately determined by the accuracy with which they can predict future AD, and therefore collecting longitudinal data is essential, with progression from MCI to AD as the key outcome of interest. To this end, our pre-clinical/MCI cohort will be followed up at 2 and 5 years after their involvement in the study, to check whether their diagnosis has converted to AD or another dementia. Diagnostic accuracies of all included biomarkers will be assessed, and we will use modelling to examine how specific biomarkers improve dementia risk prediction when combined with baseline demographic and clinical information.

Molecular classification of AD is important alongside exploration of sleep as several studies have suggested distinct interaction between different underlying AD pathology (amyloid, tau or other) and different sleep metrics e.g. [17, 25]. Only by deep characterisation of sleep phenotype as in SleepAD, can we develop clinical trials that target the right sleep treatment to the right patient.

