#### Data analysis will:

- a) Quantify the proportion of lost/degraded blood samples, and data completeness for memory tests
- b) Calculate diagnostic accuracy of the separate index tests (NFL, p-tau) for AD, at prepublished thresholds, compared to reference standard (CSF), via AUROC curves[65]
  - and explore heterogeneity in diagnostic accuracy of index tests AD by prespecified factors listed using cut offs for AD | no AD extrapolated from UCL clinical laboratories.
- Quantify the relationship between p-tau, NFL and sleep metrics in patients who have had both blood biomarkers and high-density EEG
- d) As a post hoc analysis, we will explore the diagnostic accuracy of Montreal Cognitive Assessment (MoCA) as a standard clinical test and visually compare accuracy of NFL and tau to that of MoCA.
- e) Where CSF is available, we will run biomarker analyses on the UCL research SIMOA machine to internally validate samples also tested as part of routine clinical care on the UCL clinical laboratory SIMOA machine.
- f) Once longitudinal data has been collected from our pre-clinical/MCI cohort, we will calculate the diagnostic accuracy of the separate index tests for AD via AUROC curves. The relationship between conversion to AD and the index tests will be assessed using regression models with age, sex, baseline MoCA score, plasma: CSF orexin ratio, and baseline APOE carrier status as covariables.

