#### 15 END OF STUDY

The end of the main study is defined as the last participant's last visit. The follow up medical records checks will occur at 2 and 5 years after the last participant visit.

The Investigators or the sponsor have the right at any time to terminate the study for clinical or administrative reasons.

The end of the main study will be reported to the REC, and R+D Office(s) within 90 days, or 15 days if the study is terminated prematurely. The Investigators will inform participants of the premature study closure and ensure that the appropriate follow up is arranged for all participants involved. A summary report of the study will be provided to the REC within 1 year of the end of the main study.

The end of the follow up period will also be reported in line with the above, and a further summary report provided.

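### The 2- and 5-year conversion checks are dated from the last participant, so observation time varies by up to the whole recruitment period, yet the outcome is recorded without dates and analysed without follow-up time

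*Protocol*

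**What the plan says.** All references are to the protocol.

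- **Section 1.1, Accuracy.** The text names progression from MCI to AD as the key outcome for judging blood biomarkers, and says "our pre-clinical/MCI cohort will be followed up at 2 and 5 years after their involvement in the study".
- **Section 8.2, Follow-up checks of medical records.** Records "will be checked again at 2 years and at 5 years after involvement in the study". The same paragraph then fixes the origin: "In both substudies, the date will be measured from the date of the last participant's venepuncture". The data are extracted "to identify whether the pre-clinical / MCI diagnosis has changed to a dementia diagnosis". A date of diagnosis, death or last record is not mentioned.
- **Section 15.** "The follow up medical records checks will occur at 2 and 5 years after the last participant visit". This is again a cohort-wide origin, but it is a visit and not a blood draw.
- **Section 10.2, substudy 2, item f).** Once the longitudinal data are in, "we will calculate the diagnostic accuracy of the separate index tests for AD via AUROC curves". Conversion is also related to the index tests by "regression models with age, sex, baseline MoCA score, plasma: CSF orexin ratio, and baseline APOE carrier status as covariables". Neither a horizon nor follow-up time appears.

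Prediction of progression is secondary objective 2.1.3.5. The primary objectives concern feasibility and acceptability.

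**The concern.** Two descriptions of the same follow-up do not agree. One reads as 2 and 5 years after participation. The other sets a single calendar date for everyone, counted from the last person recruited. Under the second, the first recruit is observed longer than the last by the full length of recruitment.

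That would be harmless if the date of conversion were recorded and used. As written, only a change of status is extracted, and the listed analysis has no term for time. Two people with the same disease course, both converting three years after their blood test, could then be classed differently at the nominal 2-year check. The one recruited at least a year before the end counts as a converter; the one recruited last does not.

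At stake is the meaning of the longitudinal results. Conversion proportions, and any accuracy measure labelled 2-year or 5-year, would describe a mixture of horizons set by recruitment speed. They could not be compared directly with fixed-horizon results from other cohorts.

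**Working it through.** **Is the cohort-wide origin a slip of the pen?** Section 8.2 might have meant each participant's last venepuncture. Two passages count against this. Section 15 independently counts from the last participant, and section 8.2 says substudy 2 participants have blood taken only once. The literal reading stands.

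**Observation time.** Let recruitment last R years, and let a participant be sampled u years before the last one (0 ≤ u ≤ R). At a check T years after the last venepuncture, that participant has T + u years of observation. The spread equals R.

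| R (years) | Nominal 2-year check: last / first recruit | Nominal 5-year check: last / first recruit |
|---|---|---|
| 1 | 2 / 3 | 5 / 6 |
| 2 | 2 / 4 | 5 / 7 |
| 3 | 2 / 5 | 5 / 8 |
| 4 | 2 / 6 | 5 / 9 |

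**Effect on recorded conversion.** The protocol gives no event count, conversion rate or recruitment length for this analysis, so there is no figure to reproduce. Assumptions: a constant annual conversion rate r of 5%, 10% or 15%; even recruitment; R from 1 to 4 years.

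- With λ = −ln(1 − r), true conversion by T years is 1 − exp(−λT) = 1 − (1 − r)^T.
- Recorded conversion, averaged over u uniform on 0 to R, is 1 − exp(−λT) × [1 − exp(−λR)] / (λR).

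Example with r = 10%, R = 2, T = 2: λ = 0.1054. True conversion is 1 − 0.81 = 19.0%. Recorded conversion is 1 − 0.81 × 0.19 / 0.2107 = 27.0%. For the first recruit alone it is 1 − 0.9^4 = 34.4%.

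| Check | r | True at T | R = 1 | R = 2 | R = 3 | R = 4 |
|---|---|---|---|---|---|---|
| 2-year | 5% | 10% | 12% | 14% | 16% | 18% |
| 2-year | 10% | 19% | 23% | 27% | 31% | 34% |
| 2-year | 15% | 28% | 33% | 38% | 43% | 47% |
| 5-year | 5% | 23% | 25% | 26% | 28% | 30% |
| 5-year | 10% | 41% | 44% | 47% | 49% | 52% |
| 5-year | 15% | 56% | 59% | 62% | 65% | 67% |

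The share of people counted as 2-year converters who in fact converted after their own two years is 1 − (true / recorded). For r = 10% and R = 2 it is about 30%. Across the grid it runs from 17% to 47%.

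**Effect on discrimination.** A higher conversion proportion does not itself show a biased AUROC, so this was checked separately. Assumptions: proportional hazards, a normally distributed biomarker unrelated to recruitment date, hazard ratio 1.5 to 4 per SD, and the same r and R. AUROC at the calendar check was compared with AUROC at exactly 2 or 5 years. At r = 10%, R = 3 and hazard ratio 2, the 2-year value moves from about 0.70 to about 0.71. The largest difference on the grid is about 0.014. If the measured biomarker is also assumed to drift by 0.3 SD per year over recruitment, the difference can reach about 0.04.

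**The case against.** The strongest reply is that a common calendar look-up is not an error. It guarantees every participant at least 2 and 5 years of potential follow-up, and it is compatible with starting each person's clock at their own blood test. The terms AUROC and regression models do not exclude time-dependent AUROC or Cox regression, and the choice of model commonly belongs to a statistical analysis plan, which is not to hand. This stands. A reader might infer that the protocol commits to a yes/no analysis at one fixed horizon, but it never says so.

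What the reply does not remove is the stated text. Sections 1.1, 8.2 and 15 describe the origin in ways that need reconciling. Section 8.2 also describes the extracted outcome as whether the diagnosis changed, and a later plan can use event times only if the dates are collected.

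Two further inferences are tempting and should not be drawn:

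- **Loss or death counts as non-conversion.** Section 8.2 limits the check to available records and gives no coding rule. Excluding people without records is at least as natural a reading.
- **Case-mix or assay drift confounds the result.** Nothing in the protocol shows that either drifts over recruitment.

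The reply is also right on scale. Without drift the AUROC shift is small beside the 0.08 margin that sections 4.4 and 10.1 accept for the cross-sectional AUROC. The objective is also secondary, in an observational feasibility study.

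**Conclusion.** The point holds in a limited form. The protocol gives inconsistent origins for the follow-up checks. Read literally, sections 8.2 and 15 make observation time differ between participants by up to the recruitment period. With an undated outcome and no follow-up time among the listed covariables, conversion status would depend partly on enrolment date, and 2-year or 5-year labels would be inaccurate.

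The direction is certain whenever recruitment takes time and conversion continues: recorded conversion exceeds the figure for the nominal horizon. The size rests on assumptions. Over 5-15% per year and 1 to 4 years of even recruitment, the 2-year check would record 12-47% against a true 10-28%, and the 5-year check 25-67% against 23-56%.

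Discrimination is little affected, with AUROC shifting by about 0.01 unless there is drift. The effect falls mainly on conversion proportions and on the interpretation of accuracy at a named horizon. Moderate priority: worth correcting before the first record check, but no threat to the primary objectives.

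**What to change.** 1. Reconcile sections 1.1, 8.2 and 15 so that they give one look-up rule, counted from either the last venepuncture or the last visit. Keep the two calendar look-ups.
2. State in section 8.2 that each participant's time zero is their own venepuncture, and that the dates of dementia diagnosis (with type), death and last clinical record will be extracted.
3. In section 10.2 f), define conversion at 2 and 5 years from the participant's own venepuncture. Use time-dependent AUROC, and Cox or cause-specific regression with the covariables already listed, censoring at last record or death.

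The cost is wording in four places and a few dates taken at record checks already planned, with no extra participants or visits. One limitation remains: diagnosis dates in routine records are approximate, because they show when a diagnosis was recorded and not when the condition began.
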